The sample size was generated using G*Power (Version 3.1.9.6). Using the peak power variable in a study analysing ASH and muscle soreness (Diehl, 2021), the estimate of the effect size of Cohen's d equals to 0.53 and therefore used in the sample size calculation for this proposed research. There is no further calculation to convert Cohen's d into Cohen's f to make it appropriate for ANOVA, as when there are only two groups Cohen's f is the same as Cohen's d (University of Michigan, 2021). Using ANOVA repeated measures between factors, effect size of 0.53, 80% power, 5% risk error in a two-parallel-group design and three measurements, the overall sample size is 30 participants, with 15 subjects per group. The calculation provided by G*Power can be found in the appendix.

Selection criteria

Inclusion for participants who are:

- Female
- Playing football professionally
- At a sub-elite to elite standard

- Healthy and free of disease

Exclusion for participants with:

- Active supplementation with other ergogenic aids
- Medication or contraceptives (to not interfere with existing treatment)
- Thyroid conditions (due to interaction with cortisol)
- Diabetes or certain autoimmune conditions (to not interfere with existing treatment)
- Active pregnancy (to not interfere with existing treatment)
- Allergies to nightshades such as tomato, aubergine, potatoes and peppers (as ASH is an herb in the nightshade group)
- No signing of the consent form

The withdrawal criteria will be participants who request to withdraw and do not wish to proceed, or do not complete the required study tests.

Intervention

The intervention will be 600mg of KSM-66, a branded supplement derived from the root extract of the herb ashwagandha, with a consistent rate of 5% withanolides for 28 days. It is the most clinically studied extract of the herb and is the only type of ashwagandha to receive third party testing certification (Informed Sport, Informed Ingredient, BSCG, Clean Label Project). The laboratory where the product is made, Ixoreal Biomed, has received Current Good Laboratory Practices (cGLP), quality controlled and tested against heavy metals and pesticides.

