- Improved perception of recovery
- Reduced difficulty of exertion during exercise

(Bonilla et al., 2021)

Potential side effects

Side effects of ASH are uncommon, however large doses (exceeding 1,250mg daily, based on a clinical trial examining tolerability) may induce:

- Direct irritation to the intestinal mucosa, resulting in:
 - Nausea
 - Vomiting
 - Gastrointestinal upset

(Raut et al., 2012, LiverTox, 2019)

Regarding the potential side effects of KSM-66 specifically, a trial by (Chandrasekhar et al., 2012) noted adverse effects in subjects after 60 days of 600mg KSM-66 supplementation. Overall, there were 6 adverse events with ASH and 5 with placebo. They included congestion, decreased appetite, cough and cold symptoms. The placebo group experienced fever, headache, tiredness and abdominal pain, making it unclear as to whether KSM-66 has notable or established side effects.

Intervention group

The intervention for the experimental group will be KSM-66 ashwagandha (600mg ashwagandha containing 30mg withanolides, once a day with meals for 28 days, ingested at midday) supplied by the company Zenement based in Barcelona. The branded product of KSM-66 is made by Ixoreal Biomed.

Control group

The control group will receive rice flour in a HPMC capsule, once a day with meals for 28 days, ingested at midday. The rice flour will be a commercial product found in supermarkets. To achieve randomisation, simple random allocation will be used to prevent bias amongst participants. The protocol will follow the randomisation guide by (Arifin, 2012) and will be

achieved in SPSS software. It will be a double-blind study as the main researcher will not know which participants supplement ASH or placebo.

Variables

Dependent:

Muscle strength research:

- Hand grip strength in kilograms (kg) using a CAMRY dynamometer. The variable of interest will be the mean of the right and the left-hand measurements
- Seated medicine ball throw in metres (m)
- Counter movement jump (CMJ) in watts per kilogram ($W \cdot kg^{-1}$)
- Squat jump (SJ) in centimetres (cm),
- Peak power in watts per kilogram ($W \cdot kg^{-1}$), using the results from SJ
- Rate of Perceived Exertion (RPE) via Borg Scale

Muscle recovery research:

- Perceived ratings of sleep, stress, fatigue and Delayed Onset Muscle Soreness (DOMS) via Hooper Index (HI)
- Total Quality Recovery (TQR) questionnaire
- Supplement satisfaction questionnaire

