There is high social relevance and value for the female athlete population, who are likely to experience strict training schedules with limited recovery time between training and matches. If significant benefits are found in recovery from ASH, there is a safe and low-cost method for athletes to adapt into their routine. Additionally, if there are benefits found in this thesis, practitioners who work directly with female athletes will be informed of up-to-date practice with ASH and can pass on information to athletes. Importantly, if the thesis shows no benefits across any measures, both athletes and practitioners will be informed of the supplement and its credibility.

The study holds high social and innovative relevance as it will collect, summarise and present existing published research that indicates a) overuse in high dosage and duration may lead to consistently lowered cortisol and b) consumption of solely root extraction of the herb is highly recommended in order to avoid potentially ingesting the cytotoxic metabolites of Withaferin A and Withanone, which are found in the leaves of the herb. Providing safety and information for users and future users of ASH is the crux of this thesis.

Scientific-technical validity

All of the instruments and questionnaires used in the proposed study are established in peer-reviewed literature and deemed both valid and reliable. Two measures will be taken for each tool. The first instance will be the baseline measure and will occur on-site at the training ground gym in the evening during a typical training session. The second measure will take place after 28 days of supplementation (half ASH, half placebo) in the same location and time of day. Each participant will be given a timeslot to enter the gym and perform their assessments before continuing with normal resistance-training session. The tests using instruments will be monitored by two strength and conditioning coaches, and the data will be collected by two sports scientists. The following evaluation instruments are as follows:

- Hand grip strength of the participants will be measured with a CAMRY dynamometer and the predominant measure to assess muscle strength. It is a commonly used tool in sports performance and demonstrates validity and reliability in relation to athlete

strength (Cronin et al., 2017). The validity for the use of a CAMRY dynamometer is documented by (Huang et al., 2022) when comparing against the Jamar dynamometer.

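### Simple random allocation leaves the group sizes to chance, while the sample size assumes 15 per group; a balanced list drawn once would remove a small, avoidable loss at no cost.

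*Combined protocol and SAP*

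**What the plan says.** Three places bear on this.

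- **Control group** states that "simple random allocation will be used to prevent bias amongst participants". It adds that allocation follows a cited guide and is "achieved in SPSS software". It mentions no block, restriction, fixed list or target group size.
- **Sample size** concludes that "the overall sample size is 30 participants, with 15 subjects per group". The inputs are "effect size of 0.53, 80% power, 5% risk error in a two-parallel-group design and three measurements".
- **Scientific-technical validity** places the second measurement "after 28 days of supplementation (half ASH, half placebo".

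The timetable also matters. Subjects limits recruitment to one club. Equitable selection of subjects has the study presented a month before it starts, so that players can consider it and sign consent. In the Work plan, consent is step 1, baseline strength testing is step 3 and supplements are handed out at step 5.

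**The concern.** In standard usage, simple randomisation is an independent 1:1 draw for each player. The number in each arm is then binomial. The sample size statement and the description of halves both treat it as fixed, and the text does not say how the stated procedure would deliver that.

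An uneven split lowers the precision of the between-group comparison for the same total number of players. Here that is easily avoided. The roster can be complete before anyone receives a capsule, so the usual reason for preferring simple randomisation (late allocations becoming predictable as participants enter one by one) carries little weight. What is at stake is a modest amount of power, not the validity of the comparison.

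**Working it through.** **1. The plan's own figure.** Sample size gives N = 30, two groups, m = 3 measurements, alpha = 0.05, f = 0.53 and the between-factors test. For that test the noncentrality is lambda = f² × N × m / (1 + (m − 1) × rho), with 1 and N − 2 degrees of freedom. Here rho is the correlation among a player's repeated measurements. The text does not state rho and the appendix output is not shown, so it is varied.

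At rho = 1, lambda = 0.53² × 30 = 0.2809 × 30 = 8.43 and power is 80.0%, which reproduces 30. The smallest even N for 80% power is also 30 at rho = 0.9. It is 28 at rho = 0.8, 26 at rho = 0.7 and 22 at rho = 0.5. The stated 30 therefore corresponds to a correlation near 1.

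**2. Distribution of group sizes.** With independent 1:1 allocation of 30 players, the size of one arm is Binomial(30, 0.5).

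- P(15:15) = C(30,15) / 2³⁰ = 155,117,520 / 1,073,741,824 = 0.144
- P(any other split) = 1 − 0.144 = 0.856
- P(13:17 or closer) = 0.638
- P(12:18 or worse) = 0.362
- P(11:19 or worse) = 0.200
- P(10:20 or worse) = 0.099

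**3. Loss of information.** For a split n1:n2, effective N = 4 × n1 × n2 / N. This does not depend on the effect size or on rho.

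- 12:18 gives 4 × 12 × 18 / 30 = 28.8
- 11:19 gives 4 × 11 × 19 / 30 = 27.9
- 10:20 gives 4 × 10 × 20 / 30 = 26.7

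Equivalently, effective N = N − (n1 − n2)² / N. Under simple allocation the expected value of (n1 − n2)² is N, so expected effective N = 30 − 1 = 29. The average loss is one participant, or 1/30 = 3.3%.

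**4. Effect on power.** Multiply lambda by 4 × n1 × n2 / N² and keep N = 30. The average weights each split by its binomial probability.

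| f | rho | 15:15 | 12:18 | 10:20 | Average | Average loss (points) |
|---|---|---|---|---|---|---|
| 0.53 | 1 | 80.0% | 78.4% | 75.2% | 78.6% | 1.4 |
| 0.53 | 0.9 | 82.7% | 81.1% | 78.1% | 81.3% | 1.4 |
| 0.53 | 0.7 | 88.0% | 86.6% | 84.0% | 86.8% | 1.2 |
| 0.53 | 0.5 | 92.9% | 92.0% | 89.9% | 92.0% | 0.9 |
| 0.265 | 1 | 28.9% | 27.9% | 26.2% | 28.1% | 0.8 |
| 0.265 | 0.5 | 40.4% | 39.1% | 36.7% | 39.3% | 1.1 |

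Near balance almost nothing is lost. At f = 0.53 and rho = 1, power is 79.8% at 14:16 and 79.3% at 13:17.

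The last two rows are there because Sample size asserts that "when there are only two groups Cohen's f is the same as Cohen's d". For two equal groups f = d/2, so d = 0.53 corresponds to f = 0.265. That is a separate and much larger matter. Here it only shows that the average cost of simple allocation is about 1 point on either reading.

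**The case against.** The strongest objection is that the protocol does not stop at the words simple random allocation. It points to a published SPSS guide whose steps are not reproduced. If that procedure draws a fixed number for each arm, equal groups are guaranteed and the binomial figures do not apply. The stated 15 per group and the description of halves fit that intention. This stands as a limit: from the documents one cannot tell which method will be used. In that case the wording alone is at fault, and the same sentence still needs correcting.

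Second, power is flat near balance. Simple allocation gives 13:17 or closer 64% of the time, at a cost of at most 0.7 points (80.0% to 79.3%). This also stands. A reader might infer that the power statement fails unless the split is exactly 15:15, or that allocation is what threatens 80% power. The documents support neither. The 80% baseline itself requires f = 0.53 and a correlation near 1; at rho = 0.7 or 0.5 even a 10:20 split stays above 80%, and at f = 0.265 power is far below 80% whatever the split.

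Third, a reader might infer that the trial cannot exceed 30 players. One club is named, but no squad size or enrolment cap is given. Nor is it certain that exactly 30 will consent, so a rigid list of 15 and 15 codes might not fit.

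Fourth, players may withdraw, and no allowance for this is stated. Equal allocation does not guarantee equal analysed groups. That is true, but it is no reason to begin with an avoidable imbalance.

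**Conclusion.** The point holds as a minor, free improvement. On its plain meaning, the stated method yields the planned 15:15 split with probability 14%, and a split of 10:20 or worse about one time in ten. The expected cost is one participant's worth of information. On the protocol's own input that is 1.4 points of power (80.0% to 78.6%); across the other settings examined it is 0.8 to 1.4 points.

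The conclusion assumes independent 1:1 allocation of 30 players. The power figures also assume the between-factors test, the stated f and the rho shown. The probabilities and effective sample sizes do not depend on f or rho.

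A reader might take unequal groups as a source of bias or as invalidating the analysis. Neither follows: simple randomisation is unbiased, and the planned ANOVA accommodates unequal groups.

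**What to change.** In Control group, replace simple random allocation with a sentence to this effect: after consent closes, one balanced random permutation of treatment codes is generated in SPSS for all enrolled players by a person who takes no part in data collection, so that the arms are equal in size (15:15 if 30 enrol) or differ by one if the number is odd. If the cited guide already does this, say so and drop the word simple.

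The cost is one sentence. It needs no extra players, visits, software or change to the analysis, because the roster can be known before supplements are handed out. Drawing the whole list at once and keeping it with someone outside data collection also answers the one drawback of a fixed list, that its last entries can be deduced by anyone who knows the earlier ones.

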Food diary analysis research, compared against (Dobrowolski et al., 2020):

- Energy intake (kcal)
- Energy availability (kcal/kg fat free mass/day)
- Protein (g/day)
- Carbohydrates (g/day)
- Fat (%)
- Fluids (L/day)
- Vitamin D (mg/day)
- Calcium (mg/day)
- Iron (mg/day)

All data will be collected via Snap-N-Send and stored using Nutritics dietary analysis software (Research Edition, v5.096, Dublin, Nutritics, 2019). The Snap-N-Send method was analysed in a doubly labelled water study and was shown to have enhanced validity for assessing athlete total energy intake (Costello et al., 2019). The Nutritics software was clinically studied to be a useful and valid tool for healthcare professionals to measure macronutrients and micronutrients, demonstrating that its analysis values positively correlated with plasma markers (Watkins et al., 2020)

Independent:

- The treatment of ASH: 600mg KSM66 (30mg withanolides) once a day for 28 days

Data collection

Study data will be collected manually and entered into Blanquerna's OneDrive system. All data sheets and files will be backed up on to Google Sheets and shared with associated researchers and tutors of the project. This allows for data to be reviewed by collaborators.

Dietary intake data will be collected via Whatsapp using Snap-N-Send. The data will then be manually entered and stored using Nutritics and access will be shared with collaborators.

Data analysis

For the muscle strength and recovery research, dependent variables will be described as the mean and standard deviation and calculated using and **ANOVA repeated measures, between factors** as there will be three time points. A descriptive analysis will be carried out for all the data collected in the data collection notebook. To assess the normality of the data distribution, the **Kolmogorov-Smirnov** test will be used.

For the food diary analysis, dependent variables will be described as the mean and standard deviation and determined using **one-sided t-test** to compare against data averages of nutritional recommendations for female footballers (Dobrowolski et al., 2020). **Pearson's r** will be used to examine correlations between the selected variables.

Ethical considerations

The ethical considerations for this study are predominantly the safety, comfort and consent of the participant:

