- Epistemic injustice will be avoided in the study by the researcher listening to the participant and valuing their opinion and feelings on the research subject
- The safety and tolerability of ASH has been clinically studied in humans and mice and is deemed safe to ingest. However, participants will be informed of rare, potential side effects and their right to leave the study at any time
- Personal information (name, contact details) of the participant will not be shared with a wider network or in the research papers, but will be used by the researcher during the study to check-in on the participant. They will be contacted for their questionnaire scores during the research on perceptive muscle recovery – if the participant does not agree to this method, they may decline or drop out of the study
- There will be data collection during the study, and it is important to not violate the participants right to privacy when asking personal questions via the questionnaires. The participant may decline to answer any question they deem unsuitable
- Participants will be made aware that they will be observed for the data collection during the study and may decline this if it makes them uncomfortable
- If the researcher fails to respect personal, cultural or religious values that makes the participant feel uncomfortable, they have the right to drop out of the study
- The participants will be informed about the aims of the study and will be asked to sign an informed consent form (the form can be found in the appendix)

Scientific and social value

The study is contributing to the generation of scientific knowledge. For a supplement that is widely used, the existing knowledge on its effects on athletes and females is substantially low. In addition, there is very little existing research on short-term supplementation of ASH as the focus is currently on 8-12 weeks supplementation. This study will inform as to whether the supplement can provide performance benefits after 28 days, as the author believes this is a more realistic and safer dosage duration. This research therefore holds relevance in scientific advancements and may provide new dosage guidelines to users. Another aspect of scientific

relevance is the response to the public calls for more research on this specific area of ASH and sports performance.

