There is no known conflict of interest in this study. There will be no plagiarism within this study and all words will be original to the study. There will be no fabrication or invention of results, and data will be analysed and published accurately and transparently. All collaborators will be employed staff members of the football club who are collaborating in the thesis. The gym facilities where the tests will be measured and performed are on-site of the football club and where the players have weekly gym training sessions. The gym facility is a licensed establishment. The participants will be informed of the results and will have access to their individual data.

Work plan

A visual representation of the study timeline can be found in the appendix. A description of each step is as follows:

0. Approval from the ethical committee
1. Participants are informed about the aims of the study and sign the consent form. Information about age, BMI, years of practice and health history is collected
2. Participants start tracking their food diaries via an app remotely for three days over the weekend prior to the supplementation for familiarisation
3. Baseline measures for muscle strength will be taken on the following day at the club gym, coinciding with a regular gym training session. The measures will be taken prior to starting a typical training session
4. The team will consist of the author ([name]), [name] and [name] who will assist with data collection and physiotherapist [name] who will monitor participants and their safety while performing the strength tests

5. Afterwards participants will be given a printout of the TQR questionnaire and the Hooper Index to complete for the next day. Participants will be given their course of supplementation, either placebo or KSM-66, and instructed to take one a day for 28 days
6. The following day, baseline measures for the muscle recovery will be collected remotely at midday via Whatsapp or Zoom, and at the same time participants will start supplementation of either KSM-66 or placebo
7. Fourteen days later, participants perform the muscle strength tests in the evening at the club gym. Similar to before, the team will consist of the author ([name]), [name], who will assist with data collection and physiotherapist [name] who will monitor participants' safety while performing the strength tests

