8. Afterwards participants continue with the regular gym training session. Printouts of TQR and Hooper Index questionnaires are given to participants for the next day
9. The following day muscle recovery measures are collected remotely via Whatsapp or Zoom at midday
10. An additional fourteen days later, participants finish supplementation and perform the muscle strength tests in the gym with identical circumstances (staff, equipment, temperature) as the previous two gym sessions
11. The following day muscle recovery measures are collected remotely via Whatsapp or Zoom at midday. The trial finishes
12. The analysis of data begins
13. The process dissemination of results and findings begins

The study is designed with ease of participation in mind, but there will be inconveniences for participants who forget to take the intervention or fill out the food diary. To alleviate this, participants will be notified (with permission via the consent form) over Whatsapp with reminders during the 28 days supplementation. Additionally, there will be a check-in session a week after supplementation starts, to assess participant satisfaction and compliance.

Resources

Primary resources will consist of raw data through observation obtained from gym equipment and hand grip dynamometer and first-hand accounts from participants when answering

subjective questionnaires and food diaries. Secondary resources will consist of Excel and Google sheets to store the data, SPSS software to analyse the data, and Nutritics software to analyse the dietary intake.

The facility where the baseline and post-supplementation muscle strength tests are performed will take place at the club gym for CE Seagull (located at [name]). Participants will be familiar with the facility and its equipment due to previous weekly gym training sessions prior to any measurements.

Applicability and limitations

Applicability

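### The named test compares groups over all three visits, including the pre-treatment baseline, and the plan names no group-by-time or baseline-adjusted term

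*Combined protocol and SAP*

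**What the plan says.** All references are to the combined protocol and SAP.

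- **Data analysis** gives the procedure for strength and recovery as "ANOVA repeated measures, between factors", chosen "as there will be three time points".
- **Sample size** uses the same procedure: "Using ANOVA repeated measures between factors, effect size of 0.53, 80% power, 5% risk error in a two-parallel-group design and three measurements". The result is 30 players, 15 per group.
- **Work plan** sets three visits. Step 3: "Baseline measures for muscle strength will be taken on the following day at the club gym". Step 7: "Fourteen days later, participants perform the muscle strength tests in the evening at the club gym". Step 10: "An additional fourteen days later, participants finish supplementation and perform the muscle strength tests in the gym". Steps 5 and 6 put the first capsule on the day after the baseline strength tests, at the moment the baseline recovery scores are collected. The first visit is therefore untreated.
- **Scientific and social value** states the question: "This study will inform as to whether the supplement can provide performance benefits after 28 days".
- **Scientific-technical validity** conflicts with this schedule: "Two measures will be taken for each tool", meaning baseline and day 28.

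No readable section names a group-by-time interaction, a change score, baseline as a covariate, or a day-28 contrast.

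**The concern.** In a repeated-measures ANOVA the between-factors test is the group main effect. It compares each player's mean over all visits. One of the three visits here precedes treatment, and randomisation makes the expected group difference at that visit zero. Including it pulls the estimate toward zero, and the result is not the day-28 effect that the trial asks about. Baseline, which could have removed between-player variation, instead adds noise.

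The consequences matter because the document says a null result would call the supplement's usefulness into question (Justification of the study; Scientific and social value). With 15 players per arm and a diluted test, a null result would be hard to interpret. If another ANOVA term was intended, leaving it unnamed lets the choice be made after the results are seen.

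**Working it through.** **Inputs from the plan:** 15 per arm; 5% error (two-sided assumed); visits at baseline, day 14 and day 28; d = 0.53 entered as f = 0.53.

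**Assumed, because the readable text does not give them:** SD 1, compound symmetry, and correlation ρ between visits of 0.5, 0.7, 0.8 or 0.9. The full effect d is present at days 14 and 28 unless stated.

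**1. The plan's own figure.** The between-factors calculation has noncentrality f²·N·m / (1 + (m − 1)ρ) with 1 and N − 2 df. With f = 0.53 and m = 3, the smallest even N for 80% power is 22 at ρ = 0.5, 26 at 0.7, 28 at 0.8 and 30 at 0.9 to 1.0. The stated 30 fits a high ρ, but it cannot be confirmed because the appendix calculation is not readable. For two equal groups f = d/2, so f = 0.53 means d = 1.06. Both effect sizes are shown below.

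**2. What the named test estimates.** The main effect is (0 + d14 + d28)/3.
- Full effect by day 14: 2d/3, which is 0.707 at d = 1.06 and 0.353 at d = 0.53.
- Half effect at day 14: d/2.
- Two visits only: (0 + d)/2 = d/2.

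**3. Formulas for power at 15 per arm.**
- Main effect: noncentrality (15/2)(2d/3)² / [(1 + 2ρ)/3], 28 df. Example at d = 0.53, ρ = 0.8: 7.5 × 0.1248 / 0.867 = 1.08, giving 17%.
- Day-28 ANCOVA: (15/2)d² / (1 − ρ²), 27 df. Same example: 7.5 × 0.2809 / 0.36 = 5.85, giving 65%.
- Group by time: 30·Σ(e/2)² / (1 − ρ), F(2, 56), where e are the visit differences minus their mean. Same example: 7.02, giving 63%.

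| Power at ρ = 0.5 / 0.7 / 0.8 / 0.9 | d = 1.06 | d = 0.53 |
|---|---|---|
| Main effect as written | 63 / 55 / 52 / 49% | 21 / 18 / 17 / 16% |
| Group by time | 84 / 97 / >99 / >99% | 29 / 46 / 63 / 92% |
| Day-28 ANCOVA | 90 / 98 / >99 / >99% | 37 / 50 / 65 / 89% |
| Main effect, half effect at day 14 | 40 / 35 / 32 / 31% | 14 / 12 / 12 / 11% |
| Main effect, two visits only | 37 to 30% | 13 to 11% |
| Main effect with no dilution (effect d, variance (1 + 2ρ)/3) | 93 / 88 / 85 / 83% | 40 / 35 / 32 / 31% |

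Simulation at ρ = 0.5 and 0.8 with d = 0.53 gave 20.0% and 17.3% for the main effect, and 34.8% and 62.4% for ANCOVA. The ANCOVA formula runs up to about 2 points high.

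**4. Separating dilution from the f = d slip.** The last row removes dilution. At d = 1.06, dilution alone takes power from 93–83% to 63–49%. At d = 0.53, the low undiluted power (40–31%) comes from treating f as equal to d, which is a separate error. Dilution accounts for the further fall to 21–16%.

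**5. Chance baseline imbalance.** The baseline gap between groups has SD √(2/15) = 0.37. Under compound symmetry it carries into the all-visit difference by (1 + 2ρ)/3 = 0.67 / 0.80 / 0.87 / 0.93. With no true effect, simulated rejection stays at 4.9% to 5.1% overall. It is 26 / 30 / 32 / 36% in the roughly 6% of randomisations with a gap of 0.63 to 0.83 SD. It is under 1% in the roughly 68% of randomisations where the gap is within one SD of its distribution.

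**The case against.** The strongest reply is that the phrase is a G*Power menu label. The stated reason, three time points, suits a two-group by three-visit mixed ANOVA, and SPSS normally prints the interaction as well. Nothing says that only the main effect will be read. On that reading most of the power loss disappears: group by time comes close to ANCOVA at d = 1.06 and exceeds it at d = 0.53 with ρ = 0.9 (92% against 89%). The power figures also rest on an assumed ρ, which may appear in the unreadable appendix, and on treating the cited d as a post-treatment effect. Overall type I error is unaffected.

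Much of this is fair. The author's intention is unknown, and a stated group-by-time test would be defensible. It has less power than ANCOVA if the day-14 effect is half size: 23 / 35 / 50 / 82% against 37 / 50 / 65 / 89% at d = 0.53. Two things remain. The sample size is explicitly based on the between-factors test, so the text points to that test. And if the interaction was meant, the plan neither names it nor sizes the trial on it. The assumed ρ does not change the ordering: at every value and both effect sizes in the main comparison, the test as written has the least power of the three.

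**Conclusion.** The concern holds. Read as written, the analysis estimates one half to two thirds of the day-28 effect, depending on whether half or all of it is present at day 14. That dilution follows from the visit schedule and does not depend on ρ. The power loss does: under compound symmetry, with the full effect from day 14 and ρ from 0.5 to 0.9, power is 63% to 49% instead of 90% to over 99% at d = 1.06, and 21% to 16% instead of 37% to 89% at d = 0.53. Type I error stays at 5% overall; the harm is lost precision and an estimate biased by whatever baseline imbalance occurs. On the more generous reading, the defect is that the decisive ANOVA term is not specified and the sample size is based on a different one. Either way the text needs correcting before analysis.

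**What to change.** 1. For each continuous outcome measured at baseline, replace the named test with a baseline-adjusted model. This can be a day-28 ANCOVA, or a mixed model of the day-14 and day-28 responses with baseline as covariate and group, time and group by time as terms.
2. Make the ashwagandha-minus-placebo difference at day 28, with its 95% confidence interval, the primary contrast.
3. If a mixed ANOVA is kept, state that group by time is the test.
4. Restate the power at 15 per arm for the chosen test, giving the assumed ρ.
5. Reconcile the two measures in Scientific-technical validity with the three-visit schedule used elsewhere.

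The cost is SAP wording. Baseline is already collected, SPSS fits the model, and no visit is added. The restated power may look worse: at d = 0.53 a day-28 ANCOVA with 15 per arm reaches 80% only if ρ is about 0.87 or more (78.3% at 0.86, 81.0% at 0.87). For 80% power it needs about 43 / 30 / 22 / 12 per arm at ρ = 0.5 / 0.7 / 0.8 / 0.9, against 85 / 102 / 110 / 119 for the test as written. Stating the lower power openly is enough for this fix; a larger sample is a separate decision.
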